10. STATISTICAL CONSIDERATIONS

10.1. *Sample size considerations:*

Sample size was estimated to detect a statistically significant difference in the proportion of T cells producing interferon-gamma (IFN gamma), at the 1 year time point compared with baseline using a paired t-test. A difference in proportions of 0.60 units (.2 at baseline and .8 at 1 year) would be clinically important. Assuming a common SD=0.6 at each time point, correlation between repeated measures is 0.50 and alpha = 0.05, a sample size of 10 subjects would be required to detect this difference with 80% power. Assuming 50% attrition, this study will plan to enroll a total of 15 subjects.

Notes:

- 13 subjects for 90% power with alpha=0.01
- 16 subjects for 80% power with alpha=0.01
- 19 subjects for 90% power with alpha=0.01

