No subject initiating therapy in this trial will be replaced. The stopping rules for individual subjects are as follows:

- Greater than or equal to four missed or 'no-show' appointments and four missed home doses,
- Greater than 4 instances of not having or carrying an unexpired epinephrine injector to appointments
- Anaphylactic reaction listed as a Grade 4 as defined by the World Allergy Organization grading scale for systemic reactions to immunotherapy related to peanut OIT dosing at any stage of the protocol.
- Any participant is diagnosed with eosinophilic esophagitis
- Any participant is diagnosed with moderate to severe asthma based on the NHLBI guidelines
- Any participant needs treatment with greater than medium daily doses of inhaled corticosteroids, as defined by the NHLBI guidelines
- Any participant has an accidental peanut ingestion with anaphylaxis during the time on oral desensitization

Participants may be prematurely terminated from the study if:

- The participant elects to withdraw consent from all future study activities, including follow-up
- The participant is “lost to follow-up” (i.e., no further follow-up is possible because attempts to reestablish contact with the participant have failed)
- The participant dies

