9. MEASUREMENT OF EFFECT

9.1. Response Review:

The Data Safety Monitoring Committee will review the responses to the primary and secondary objectives every 6 months during the trial.

9.2. Response Criteria:

9.2.1. The primary objective will be measured by recording the daily symptoms experienced by the subjects and the number of subjects with no clinical symptoms during 6 g peanut flour challenge at time 50 weeks compared to time 0 weeks. The change in tolerated dose will be assessed between baseline and one year. The proportion of patients who tolerate 6 g of peanut flour will be compared at baseline and at the one year point using McNemar's test for matched pair data. The proportion of subjects will be estimated with exact binomial confidence intervals.

9.2.2. For the first secondary objective, flow cytometric analysis of T, NKT cells, and basophils will be performed through the measurement of the percent of cells producing a

cytokine as well as measuring surface and intracellular markers expressed upon activation and the significance of changes from time 0 to 1 year will be assessed as described below by using a paired t-test of the log-transformed data. Baseline measures of cell activation will be summarized by means with standard deviation. Normality will be assessed by quantile-quantile plots, and non-normality will be addressed by data transformations. A general linear mixed model will be used to estimate the effect of the therapeutic procedure over time. The model will include a fixed effect for time (discrete), and the matrix of correlated error terms will assume a first-order autoregressive structure. Alternative correlation structures such as the unstructured and compound symmetry will be considered. Correlation structures will be assessed by Akaike's Information Criteria. The likelihood ratio test will be used to test for overall significance of the model. P-values will be adjusted using the Holm's step down Bonferonni correction for multiple comparisons. Activation responses that are significant at the 0.05 level after adjustment will be further assessed. Pairwise comparisons between discrete time points will be tested for significant differences, and p-values will be adjusted using the Bonferonni correction. Statistical significance of the adjusted p-values will be assessed at the 0.05 level.

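### Section 10.1: enrolling 15 with 50% attrition does not leave the 10 evaluable subjects required; one note carries the wrong alpha, and the scale of the SD is not stated

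*Combined protocol and SAP*

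**What the plan says.** Section 10.1 sizes the study on a paired t-test of the proportion of T cells producing IFN-gamma, 1 year against baseline. The effect is "A difference in proportions of 0.60 units (.2 at baseline and .8 at 1 year"), and the variability is "Assuming a common SD=0.6 at each time point", with correlation 0.50 and alpha 0.05. From these, "a sample size of 10 subjects would be required to detect this difference with 80% power". Enrolment follows: "Assuming 50% attrition, this study will plan to enroll a total of 15 subjects".

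Three notes give alternatives. The first is "13 subjects for 90% power with alpha=0.01" and the third is "19 subjects for 90% power with alpha=0.01". The second gives 16 subjects for 80% power at alpha 0.01.

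Three other sections bear on this:

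- Section 9.2.2 tests the change from time 0 to 1 year "by using a paired t-test of the log-transformed data". It gives no log base.
- Section 6.11 says "No subject initiating therapy in this trial will be replaced".
- Section 6.12 keeps participants who stop treatment in the study and continues mechanistic blood draws in those who are willing.

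**The concern.** Three things in Section 10.1 do not fit together, and they differ in weight.

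1. **Attrition.** The step from 10 to 15 adds half of 10. Losing half of 15 does not leave 10. This is the substantive point, because the stated 80% power rests on 10 evaluable subjects.
2. **First note.** Two different sample sizes are given for the same power and the same alpha.
3. **Scale.** The effect is worded as a change in a proportion, but the SD is larger than any such proportion can have. Section 9.2.2 tests the same change on a log scale, and Section 10.1 mentions no transformation.

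This is the only sample size justification in the protocol. At stake is whether a reader can rely on the stated power, and can tell what variability was assumed.

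**Working it through.** **Inputs (Section 10.1):** difference 0.60, SD 0.6 at each time, correlation 0.50, alpha 0.05. Sidedness is not stated. Two-sided is assumed because it reproduces the plan's 10, 16 and 19; a one-sided test gives 8, 13 and 16 for those three cases.

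**Step 1: reproduce the plan's 10.**

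- SD of the difference = sqrt(0.36 + 0.36 - 2 x 0.5 x 0.36) = 0.6.
- Standardised effect d = 0.60/0.6 = 1.0.
- Exact paired t-test power (noncentral t, n - 1 degrees of freedom, noncentrality d x sqrt(n)): 74.8% at n = 9 and 80.3% at n = 10.

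The 10 is correct on its inputs.

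**Step 2: attrition.**

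- 10 x 1.5 = 15, the plan's figure.
- 1 - 10/15 = 33.3%, the loss that 15 can absorb while leaving 10.
- 15 x 0.5 = 7.5, so 7 or 8 remain at 50% loss.
- 10/(1 - 0.5) = 20, the enrolment that leaves 10 at 50% loss.

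| Paired samples at 1 year | Power, two-sided alpha 0.05 |
|---|---|
| 10 | 80.3% |
| 8 | 68.1% |
| 7 | 60.0% |

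The last two rows assume that the 50% is loss of the 1-year paired sample.

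**Step 3: the notes (d = 1.0, two-sided).**

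| Power | Alpha | Required n | Plan |
|---|---|---|---|
| 90% | 0.05 | 13 | 13, but labelled alpha 0.01 |
| 80% | 0.01 | 16 | 16 |
| 90% | 0.01 | 19 | 19 |

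With 13 subjects, power is 91.1% at alpha 0.05 and 70.1% at alpha 0.01. The first note is right only for alpha 0.05.

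**Step 4: the scale.**

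- For a variable between 0 and 1 with mean p, the largest SD is sqrt(p(1 - p)). At p = 0.2 or 0.8 this is sqrt(0.16) = 0.4, so 0.6 cannot occur on the proportion scale.
- The correlation tightens this further. The covariance is at most 0.2 - 0.2 x 0.8 = 0.04, so a common SD with correlation 0.5 cannot exceed sqrt(0.04/0.5) = 0.283.
- On a log10 scale the same change is log10(0.8/0.2) = 0.602, and d = 0.602/0.6 = 1.003. An SD of 0.6 is feasible there. Required n is again 10, 13, 16 and 19. Power is 80.6% at n = 10, 68.4% at n = 8 and 60.3% at n = 7.
- On a natural-log scale the change is 1.386 and d = 1.386/0.6 = 2.31. Required n would be 4, 5, 6 and 7, none of which matches the plan, and power at n = 7 would be 99.9%.

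**The case against.** The strongest reply concerns what attrition means. Section 6.12 continues mechanistic blood draws in willing subjects who stop treatment, and the powered endpoint is a mechanistic blood measure. The comparison is at 1 year, whereas participation runs for 38 months (Section 1) or about 40 months (Section 6). Some of the assumed 50% could therefore stop treatment or leave late and still supply a 1-year sample. This stands as a condition: the 60% to 68% applies only if the 50% are missing from the 1-year pair. It does not rescue the inflation step, because Section 10.1 applies the 50% to this very endpoint and its enrolment figure does not follow from it.

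A second reply is that Section 9.2.2 does name a log scale for the same test, so an SD of 0.6 may be only unlabelled. That also stands. A reader might infer from Section 10.1 alone that the calculation rests on an impossible SD and has no valid basis. The documents do not support that reading, since log10 inputs are feasible and reproduce every stated sample size. Nor do they establish that log10 was meant: no base is given, and 0.8 - 0.2 is also 0.60.

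Third, the first note is evidently a slip. It does not determine the enrolment of 15, and the main text states alpha 0.05. Agreed; that part is editorial.

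**Conclusion.** The point holds, within limits. On its own attrition figure, Section 10.1 does not deliver the 10 evaluable subjects behind its 80% power. With 50% of the 1-year paired samples lost, 7 or 8 remain and power is 60% to 68%. This rests on the stated inputs, a two-sided test at alpha 0.05, and no replacement. It is nearly unchanged on a log10 reading. It would not hold on natural logs, but that reading does not reproduce the plan's sample sizes.

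The first note carries the wrong alpha. The scale of the 0.60 and the SD is unstated and needs reconciling with Section 9.2.2.

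A reader might conclude that the trial is underpowered. The documents do not show that. The calculation covers one marker within a secondary mechanistic objective, the actual loss of 1-year samples is unknown, and the primary objective of safety and tolerated dose is not sized here. What fails is the written justification. It should be fixed, but it does not threaten the trial.

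**What to change.** Keep the enrolment of 15 and revise Section 10.1 as follows:

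1. Say that attrition means loss of the 1-year paired sample, with reference to the continued blood draws in Section 6.12.
2. State that 50% loss leaves 7 or 8 subjects with 60% to 68% power, and that 80% power holds only if no more than one-third are lost. One-third is simply what 15 can absorb. Nothing in the documents supports it as an expectation, so use it as the planning assumption only with a justification.
3. Change alpha in the first note to 0.05.
4. State the scale and log base of the 0.60 and the SD 0.6, consistently with Section 9.2.2. If they are log10 values, the power figures above stand for the unadjusted test. If not, give an SD that is attainable on the analysis scale and compatible with the assumed correlation, and restate the power.

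The cost is wording, plus one recalculation if the inputs are not log10 values. No patients are added and no analysis changes. The downside is that either the stated power or the stated attrition allowance becomes less favourable.

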11. PROTECTION OF HUMAN SUBJECTS

Potential benefits if the therapy is tolerated include: the potential decrease in the subject's reactivity to peanuts after an accidental ingestion of peanut, altering the natural progression of peanut allergy, becoming clinically and immunologically tolerant to peanut, which is otherwise not likely to happen, and the ability to broaden their diet and lead a more normal life without the restrictions caused by having a potentially severe food allergy. This study will also help to expand the knowledge of food allergy in general and may lead to new management and therapeutic protocols for individuals with other food-allergies.

All data will be kept on secure internal databases on the Texas Children's Hospital and Baylor College of Medicine servers. The files will be password protected and deleted at the earliest possible convenience. When feasible, all data will be stripped from identifiers to reduce the risk of patient identifiable information from being intercepted by unauthorized parties. Our research team knows and understands that it is our responsibility to protect patient records and personal information and will fully abide to HIPAA regulations.

The subjects will not be financially responsible for any research-related clinic visits, procedures, or peanut oral immunotherapy. Standard of care clinic visits and laboratory and diagnostic tests, however, will have to be covered by the patient or patient's insurance.

Participation will be voluntary and will require informed consent by the patient or his/her legally authorized representative, parent, or guardian according to state regulations. The patient

and family will have to be fully aware of potential worsening of symptoms when even life-threatening conditions may emerge necessitating surgical and/or intensive care interventions.

12. ADVERSE EVENTS

12.1. *Adverse Event (AE) or Medical Event:*

An adverse event is a new, undesirable medical event or occurrence or worsening of an existing condition (including an abnormal laboratory finding) in a subject that occurs during treatment and throughout the study, whether or not it is considered to be study related. This includes the following:

- AEs not previously observed in the patient that emerge during the protocol-specified AE reporting period, including signs or symptoms associated with peanut allergy that were not present prior to the AE reporting period
- Complications that occur as a result of protocol-mandated interventions (e.g., invasive procedures such as biopsies)
- If applicable, AEs that occur prior to assignment of study treatment associated with medication washout, treatment run-in, or other protocol-mandated intervention
- Preexisting medical conditions (other than the condition being studied) judged by the investigator to have worsened in severity or frequency or changed in character during the protocol-specified AE reporting period

Potential adverse reactions seen in subjects treated with peanut OIT and subjects undergoing DBPCFC include the following: skin manifestations such as pruritus, urticaria, or angioedema; respiratory symptoms such as wheezing, coughing, nasal congestion/rhinorrhea, cough and hoarseness; and gastrointestinal manifestations such as vomiting, diarrhea, or abdominal pain. Anaphylaxis is a potential risk involving any of the above symptoms plus hypotension and circulatory collapse.

12.2. *Serious Adverse Event:*

A serious adverse event is defined as any adverse therapy experience occurring at any dose that results in the following:

- Death: A death occurring during the study, or which comes to the attention of the investigator during the protocol-defined follow-up after the completion of therapy whether or not considered treatment related, must be reported.
- Life-threatening: Any adverse therapy experience that places the subject or subjects, in the view of the investigator, at immediate risk of death from the reaction as it

occurred (i.e., it does not include a reaction that had it occurred in a more serious form, might have caused death).

- In-patient hospitalizations or prolongation of existing hospitalization.
- Persistent or significant disability or incapacity.
- Congenital anomaly/birth defect.
- An event that required intervention to prevent permanent impairment or damage.

All AEs that do not meet any of the criteria for serious should be regarded as non-serious AEs.

Each recorded AE or SAE will be described by its duration (i.e., start and end dates), severity, regulatory seriousness criteria if applicable, suspected relationship to the investigational product (see below), and actions taken.

12.3. Expected adverse event and unexpected adverse event:

Expected adverse events are those that have been previously identified as resulting from administration of the agent. For purposes of this study, an adverse event is considered expected when it is included in the protocol and informed consent document as a potential risk.

An adverse event is considered unexpected when it varies in nature, intensity, or frequency from information provided in the current adverse event list in the protocol and informed consent document as a potential risk.

12.4. Toxicity Grading

The terms “severe” and “serious” are not synonymous. Severity refers to the intensity of an AE (as in mild, moderate, or severe pain); the event itself may be of relatively minor medical significance (such as severe headache). “Serious” is a regulatory definition and is based on patient or event outcome or action criteria usually associated with events that pose a threat to a patient’s life or vital functions. Seriousness (not severity) serves as the guide for defining regulatory reporting obligations.

Toxicity grades are assigned to indicate the severity of adverse experiences and toxicities using The World Allergy Organization (WAO) as displayed in Table 8. The World Allergy Organization (WAO) (44) has been reviewed specifically for this protocol and is otherwise appropriate for this study population. The purpose of using the WAO system is to provide standard language to describe toxicities and to facilitate tabulation and analysis of the data and assessment of the clinical significance of treatment-related toxicities. The NCI-CTCAE grading system will be used for all adverse events except for allergic reactions, for which the WHO criteria will be used.

Table 8. Grading System for Adverse Event Allergic Reactions

Current grading systems for allergic reactions used by World Allergy Organization for allergic reactions to immunotherapy as displayed below. (17)

Grade 1 Mild	Grade 2 Moderate	Grade 3 Severe	Grade 4 Life threatening	Grade 5 Death

Symptom(s)/ sign(s) of one organ system present
 
Cutaneous
 
Generalized pruritus, urticaria, flushing or sensation of heat or warmth
 
or
 
Angioedema (not laryngeal, tongue or uvular)
 
or
 
Upper respiratory
 
Rhinitis (e.g., sneezing, rhinorrhea, nasal pruritus and/or nasal congestion)
 
or
 
Throat-clearing (itchy throat)
 
or
 
Cough perceived to come from the upper airway, not the lung, larynx, or trachea
 
or
	
Symptom(s)/ sign(s) of more than one organ system present
 
or
 
Lower respiratory
 
Asthma: cough, wheezing, shortness of breath (e.g., less than 40% PEF or FEV1 drop, responding to an inhaled bronchodilator)
 
or
 
Gastrointestinal
 
Abdominal cramps, vomiting, or diarrhea
 
or
 
Other
 
Uterine cramps
 
_____
	
Lower respiratory
 
Asthma (e.g., 40% PEF or FEV1 drop, NOT responding to an inhaled bronchodilator)
 
or
 
Upper respiratory
 
Laryngeal, uvula or tongue edema with or without stridor
	
Lower or Upper respiratory
 
Respiratory failure with or without loss of consciousness
 
or
 
Cardiovascular
 
Hypotension with or without loss of consciousness
	
Death

Conjunctival Conjunctival erythema, pruritus or tearing				
Other Nausea, metallic taste, or headache				

Relationship to Procedure Definitions

Associated: There is a reasonable possibility that the adverse event may have been caused by the test product and/or procedure. This definition applies to those adverse events that are considered definitely, probably or possibly related to the procedure.

1. **Definitely related:** An adverse event that follows a temporal sequence from administration of the test product and/or procedure; follows a known response pattern to the test article and/or procedure; and, when appropriate to the protocol, is confirmed by improvement after stopping the test product (positive re-challenge: and by reappearance of the reaction after repeat exposure [positive re-challenge]); and cannot be reasonably explained by known characteristics of the subject’s clinical state or by other therapies.
2. **Probably related:** An adverse event that follows a reasonable temporal sequence from administration of the test product and/or procedure; follows a known response pattern to the test product and/or procedure, is confirmed by improvement after re-challenge; and cannot be reasonably explained by the known characteristics of the participant’s clinical state or other therapies.
3. **Possibly related:** An adverse event that follows a reasonable temporal; sequence from administration of the test product and/or procedure and follows a known response pattern to the test product and/or procedure, but could have been produced by the participant’s clinical state or by other therapies.

Not associated: An adverse event for which sufficient information exists to indicate that the etiology is not related to the test product and/or therapy.

Unrelated: An adverse event that does not follow a reasonable temporal sequence after administration of the test product and/or procedure and most likely is explained by the participant’s clinical disease state or by other therapies. In addition, a negative re-challenge to the test article and/or procedure would support an unrelated relationship.

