Any extra serum will be stored in a freezer in the Allergy and Immunology laboratories at Texas Children's Hospital in Houston.

The sample will be labeled with the subject's unique identifier number. The subject's name and personal information will not be included on the label. The link to the unique identifier number will be stored in a binder in [name] office in a locked cabinet in Houston.

The samples will be accessible by [name] and other study personnel.

If samples are used for reasons apart from those listed in this study (measuring food-specific IgE, IgG and IgG4, cellular immune studies) a study protocol will be submitted and an approval must be granted by the Institutional Review Board (IRB) of Baylor College of Medicine before the serum can be used.

6.10. Criteria for Premature Termination of the Study (Stopping Rules):

Potential adverse reactions seen in subjects treated with peanut OIT and subjects undergoing DBPCFC include the following: skin manifestations such as pruritus, urticaria, or angioedema; respiratory symptoms such as wheezing, coughing, nasal congestion/rhinorrhea, cough and hoarseness; and gastrointestinal manifestations such as vomiting, diarrhea, or abdominal pain. Eosinophilic esophagitis, an allergic gastrointestinal disease, can also occur. Anaphylaxis is a potential risk involving any of the above symptoms plus hypotension and circulatory collapse.

The study will be stopped and reviewed by the Principal Investigator and the IRB if:

- Any death (grade 5) related to peanut OIT dosing
- Greater than 2 anaphylactic reactions listed as a Grade 4 as defined by the World Allergy Organization grading scale for systemic reactions to immunotherapy related to peanut OIT dosing at any stage of the protocol. All patients will stay at their highest tolerated dose until the study re-opens.
- Greater than 3 subjects that require greater than 1 injection of intramuscular epinephrine during oral dose escalation or maintenance of the peanut flour
- Greater than 2 cases of new onset eosinophilic esophagitis

The Principal Investigator and Co-Investigators are responsible for collecting and recording all clinical data. As these results are collected, all toxicities and adverse events will be identified and reported to the principal investigator. The Principal Investigator will determine relationship of the event to the study intervention and decide course of action for the study participant.

6.11. Participant Withdrawal Criteria:

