- A. For a Grade 1 reaction, the daily dose will be continued until the next visit. If a subsequent Grade 1 or greater reaction occurs, the participant will hold future doses and return to the clinic within 48 hours and be challenged to the previous tolerated dose.
- B. For a Grade 2 and 3 reaction, the participant will hold all future doses and return to the clinic within 48 hours to be challenged to the previous tolerated dose. If a Grade 3 reaction occurs greater than 2 times, the participant's dose will remain at the highest tolerated dose and will enter the maintenance phase of the study.
- C. Grade 4 reaction will cause discontinuation of the study for that patient and the patient will be given the option to be converted to a peanut equivalent dose.

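### Section 12.4 inverts the re-challenge criterion for relatedness: no reaction on re-exposure confirms 'probably related' and also supports 'unrelated' (minor)

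*Combined protocol and SAP*

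**What the plan says.** Section 12.4 (Relationship to Procedure Definitions) uses re-exposure in three places.

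- *Definitely related*: where the protocol makes confirmation appropriate, the event "is confirmed by improvement after stopping the test product (positive re-challenge: and by reappearance of the reaction after repeat exposure". Improvement on stopping is thus labelled a positive re-challenge, and reappearance on repeat exposure is asked for as well.
- *Probably related*: the event "is confirmed by improvement after re-challenge; and cannot be reasonably explained by the known characteristics of the" child's condition or by other treatment. There is no exemption for events that were never re-challenged.
- *Unrelated*: the lead criterion is "An adverse event that does not follow a reasonable temporal sequence after administration of the test product and/or procedure", together with a most likely explanation in the child's disease or other treatment. The text then adds that "a negative re-challenge to the test article and/or procedure would support an unrelated relationship".

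*Possibly related* requires that the event could have come from the child's condition or another therapy. An umbrella category, *associated*, pools definite, probable and possible events.

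The dose-adjustment algorithm in Appendix II says that after a Grade 2 or 3 reaction the participant "will hold all future doses and return to the clinic within 48 hours to be challenged to the previous tolerated dose". A second reaction after a first Grade 1 reaction leads to the same kind of challenge. Nothing in Section 12.4 or Appendix II says how these challenges count towards relatedness.

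**The concern.** Causality assessment rests on two separate observations. De-challenge asks whether the event abates when the product is stopped or reduced. Re-challenge asks whether it returns on renewed exposure. Abating on the first and returning on the second both point to the product. Section 12.4 mixes the two terms, and in *probably related* the direction is reversed: improvement on re-exposure is made the confirming sign.

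With infrequent re-exposure this would be a slip with little effect. In this trial re-exposure is the standard response to a Grade 2 or 3 dosing reaction, so an assessor will often hold a re-challenge result and look to the definitions for what it means. The Principal Investigator alone determines relatedness (Section 6.10, stopping rules), so the written definitions are the main safeguard for consistent coding. At stake are the sub-category reported in the safety tables and, for events with a possible alternative cause, whether the event is coded as treatment-related at all.

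**Working it through.** There is no stated figure to reproduce. The check compares the texts, with one small calculation.

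**Step 1. What each observation does under each definition, read literally.** 'Improvement after re-challenge' is taken to mean no reaction, or a lesser one, on re-exposure.

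| Observation | *Definitely* | *Probably* | *Unrelated* |
|---|---|---|---|
| Improves after stopping | counts towards it, under the wrong label | not mentioned | not mentioned |
| Reaction returns on re-exposure | counts towards it | confirming clause fails | no support |
| No reaction on re-exposure | confirming clause fails | confirming clause met | supported |
| No re-exposure done | still possible, since confirmation is conditional | confirming clause fails | depends on timing and explanation |

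The third row is the contradiction: one result confirms *probably* and supports *unrelated*. The second row is the inversion: recurrence, the stronger evidence, fails *probably*. The fourth row is a gap: a time-linked, unexplained reaction without re-challenge can be *definitely* but not *probably*. It does not fit *possibly* either, because that category needs another potential cause.

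**Step 2. What the Appendix II challenge can show.** The previous tolerated dose is not defined. Assume that in build-up it is the preceding step of Table 3. The ratio of challenge dose to reaction dose is then (preceding step) / (current step):

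- smallest: 120 / 240 = 50% (the four doublings from 1.8 mg to 28.8 mg give the same value);
- largest: 3600 / 3900 = 92%.

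Under this assumption every such challenge is at a lower dose than the one that caused the reaction. Tolerating it is what a true dose-related reaction would predict, so it is weak evidence against causation. For a reaction in maintenance, or to a dose tolerated on earlier days, the documents do not say which dose is meant.

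**Step 3. Where relatedness is used.**

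- Follow-up (Section 12.5): serious events and treatment-related events ongoing at the end of study are followed to resolution. Other new events are followed for 30 days after the last dose. A non-serious event moved to *unrelated* therefore loses open-ended follow-up.
- Safety tabulation (Section 12.4): the grading is meant to support assessment of treatment-related toxicity.
- Reports to FDA (Section 12.6): these need a serious or life-threatening event that is unexpected and at least possibly related.
- Study stopping rules (Section 6.10): the death and Grade 4 rules depend on relatedness; the Grade 4 rule counts reactions "related to peanut OIT dosing at any stage of the protocol". The epinephrine and eosinophilic esophagitis rules contain no relatedness test.

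**The case against.** The best defence is that this is a slip of 're-challenge' for 'de-challenge', visible from the parallel text in *definitely*, and that a competent assessor would read through it. The slip is the likely cause, which makes this a wording error and not a design choice. It still needs correcting, because the protocol generates re-exposure results routinely and gives no other instruction for using them.

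The defence is stronger on consequences, and several larger readings are tempting but unsupported.

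- *A reader might infer that one event can satisfy both categories.* It cannot. *Unrelated* needs an unreasonable time sequence and a likely alternative explanation; *probably* needs the reverse of both. A negative re-challenge only adds support.
- *A reader might infer that the stopping rules are compromised.* Grade 4 reactions lead to discontinuation under Appendix II, not to the clinic challenge, so that challenge cannot alter the Grade 4 or death counts.
- *A reader might infer that the primary safety result is affected.* Section 9.2.1 measures the primary objective by daily symptoms, the 6 g challenge and the change in tolerated dose. It defines no treatment-related rate.
- *A reader might multiply the frequencies in Section 7 by 15 children*: 15 × 0.20 = 3 and 15 × 0.29 = 4.4. These are not counts of affected children. The 29% is for an initial escalation day and includes nausea, which is Grade 1 in Table 8. The list covers food challenges as well as therapy. The Appendix II sheet scores a single vomiting episode as mild, whereas Table 8 makes vomiting Grade 2.

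Two further limits stand. The gap in the fourth row of the table concerns the sub-label, since *associated* still captures a plausible, time-linked reaction. The effect on FDA reports is small, because symptoms such as vomiting are listed risks and hence expected in nature.

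**Conclusion.** The point holds as a wording error of minor severity. In Section 12.4 the re-challenge criterion is inverted in *probably related*, mislabelled in *definitely related*, and in conflict with *unrelated*. The likely effect is miscoding between definite, probable and possible. For ambiguous events with a possible alternative cause, a tolerated Appendix II challenge could also be taken as support for *unrelated*, with shorter follow-up for non-serious events. The documents do not allow the number of such events to be estimated.

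The contradiction rests on the text alone. Its practical weight rests on two assumptions: that assessors apply the wording literally, and that the previous tolerated dose in build-up is a lower step of Table 3. Appendix II does not itself call the dose lower, and its algorithm belongs to desensitization and dose escalation; Section 6.3 sets no such re-challenge after a reaction in the entry food challenge.

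**What to change.** Amend three definitions in Section 12.4:

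1. *Definitely related*: call improvement after stopping a positive de-challenge, and keep the term positive re-challenge for reappearance on repeat exposure.
2. *Probably related*: replace improvement after re-challenge with improvement after the product is stopped or reduced. Add the qualifier that *definitely* already carries, so that a time-linked, unexplained reaction qualifies without any re-challenge.
3. *Unrelated*: state that tolerating an Appendix II challenge at a dose below the one that caused the reaction does not count as a negative re-challenge.

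These are coding definitions only. The cost is a few sentences, plus any case report form guidance that repeats them. No dose, visit, challenge procedure or sample size changes, and no extra challenge is added.
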